3.3. Compliance

Compliance will be based upon patient-reported usage. The degree of compliance is an important factor for interpreting the results of the ITT analysis as well as serving the basis for per protocol analyses. However, as noted by Wittes, analyses relying on post-randomization variables are likely to be biased and/or require complex mathematical models with numerous assumptions.⁵⁵

Individuals will be classified according to a number of different methods (e.g. any compliance [at least one usage], minimum compliance [above a certain threshold]) for sensitivity analyses. A variety of causal inference techniques, including inverse probability weighting methods similar to those described by Murray and Hernan, will be used to assess the impact of adherence.⁵⁶ In addition, prescription data will be available for a subset of patients from Medicare claims files via the collaboration with the FDA Sentinel Program. These data will be compared with the self-reported data to help guide the planned compliance analyses.

3.4. Missing Data

As noted in the IOM Guidelines, prevention is the most important method for handling missing data.⁵⁷ The recommended strategies include careful consideration of potential barriers to data collection during the design phase of the trial, including patient and outcome selection. For example, an advantage to our choice of the primary outcome, all-cause hospitalization or death, is that it can be measured and confirmed from numerous sources. The primary source of outcome data will be from patients. In addition, we have planned a number of strategies to limit missing data during the execution of the trial. As noted above, we will rely on several sources of data to ascertain the primary outcome measures of all-cause hospitalization and mortality including patient reports supplemented by administrative data from CMS and the NDI and follow-up data collected by Site Coordinators. For patient-reported outcomes, we will employ several strategies to prevent missing data, including collection of multiple contacts, verification of phone numbers, email addresses, and secondary contacts including relatives or neighbors, and healthcare providers. Patients will be reminded about outstanding questionnaires via emails and texts backed-up with phone calls. Clinical centers will review the EHR periodically and administrative sources will also be used to identify unreported events. If we are unable to contact the patient via those measures, Site Coordinators will be asked to “find” those patients and collect the missing data. We will also employ real-time data performance reporting so that we can monitor trends in missing data to identify problems and develop interventions. Data on treatment adherence and outcomes will be extracted from CMS administrative database on the subset of patients enrolled in Medicare via a collaboration with the FDA Sentinel Program. We will also use the NDI to identify unreported

Protocol Version 4.0

deaths in the entire study group.

All patients will be accounted for in analyses. For the primary outcome (hospitalization or death), a Cox proportional hazards model will be used. Individuals who are lost to follow-up are censored at the time of the last known contact and so all individuals with follow-up may be included in the analyses. Data collected up until the time of withdrawal will be retained from those participants who do not continue on in the study. Issues with missing data arise if the censoring mechanism is related to the outcome of interest. The range of potential influence will be established by imputing the 'best' and 'worst' case scenarios. Analytic methods will be used to assess the censoring patterns. Based upon these findings, sensitivity analyses using multiple imputation, inverse probability weighting, or a pattern mixture approach will be used.^{46,47} For non-time to event outcomes, the primary analysis will be based upon mixed effects models (for replicate measurements over time) or multiple imputation (for single measurements), both of which are robust to data that is missing at random. 'Best' and 'worst' case analyses similar to those used for time-to-event outcomes will also be used to gauge the potential effect of missing data.

Reasons for missing data will be assessed for all data sources. For data collected from clinical centers, the reason for missing data will be collected directly from the clinic, e.g., data not assessed, patient refused or no follow-up for patient at the clinical center. The Call Center will record attempts to remind and collect data for patient-reported outcomes. These will include patient refusal, inability to contact patient, or death. In comparative effectiveness trials where the hypothesis is non-inferiority, treatment cross-overs, treatment cessation, lack of adherence, and loss to follow-up tend to support the inference of non-inferiority between treatment groups. To some extent, these deviations from protocol are the rationale for conducting a "real-world" pragmatic trial. Interpretation of these factors can be assisted by comparison of as randomized and per protocol analyses as well as sensitivity analyses of specified subgroups. However, failure to ascertain the primary outcome, particularly if there is differential data loss between treatment groups is a serious threat to the validity of the trial and there is no analytic technique that can completely overcome this. In this trial, we are proposing to use multiple data streams including EHRs, directly from patients and providers, and from CMS administrative datasets and NDI administrative datasets for the primary outcome, we should be able to have virtually complete ascertainment of hospitalizations and deaths for this largely Medicare population.

Protocol Version 4.0

3.5. Interim Analysis

A single, formal, interim efficacy analysis will be performed once 50% of the information has been collected (i.e., 684 of the expected 1368 event of hospitalization or death have been observed).

The trial will be stopped early only if one of the two treatments is demonstrated to be superior, i.e. it will not stop if the non-inferiority criteria are met. Based upon an O'Brien-Flemming type boundary, the type I error rate would be 0.00305 for the interim analysis and 0.04695 at the final analysis to maintain a global 0.05 error rate over the course of the trial for the superiority comparison.

Protocol Version 4.0

4. Human Subjects

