3.1. Sample Size

RELIANCE is a randomized, pragmatic, comparative effectiveness trial designed to evaluate whether azithromycin is non-inferior to roflumilast in high-risk patients with COPD for prevention of hospitalizations or death. Our choice of a non-inferiority margin of 1.2 was based upon a recently completed clinical trial in COPD, as well as opinions solicited from clinicians and patients^{48,49}. In a survey of 48 clinicians, the minimum clinically important difference was identified to be 1.2 or higher by 75% of the survey participants and the margin of 1.2 was the most commonly selected (33%). An online survey of 50 patients conducted by the COPD PPRN identified a range of different effect sizes, which seemed to vary based on the history of previous COPD exacerbations, and hospitalizations, and tolerance for adverse effects. A margin of 1.2 is within the range of interest expressed by patients. The planned recruitment period is 30 months with an additional 6 months of follow-up. A sample size of 3,200 provides 92% power with a 1-sided type I error of 0.025 to establish non-inferiority based upon a log-rank test with a margin of HR = 1.2 (azithromycin: roflumilast) assuming: (1) the true HR = 1, (2) the cumulative percent with an event at 1 year is 30%, and (3) a 5% loss to follow-up per year (14.3% cumulatively). Post-hoc analyses of trials suggest that while roflumilast appears to benefit both past and current smokers, the benefits of chronic azithromycin may be limited to past smokers.^{34,50} Accordingly, we will monitor treatment outcomes stratified by current vs. former smoking status and present these results to the DSMB to evaluate the relative safety/efficacy of the two treatments. If the lower bound of the 99% CI for azithromycin exceeds 1.5 at any interim analysis, we will recommend to the SC that the current smoking strata be terminated. The sample size of 3,200 participants provides 89% power to detect a heterogeneous effect based upon smoking status (HR = 1 for roflumilast vs HR = 1.538 for azithromycin for current vs former smokers) assuming a reference cumulative incidence of 30% at one year for current smokers in both treatment groups, equal recruitment to all four subgroups, 5% loss to follow-up per year (14.3% cumulatively) and a two-sided type I error rate. These analyses were computed using PASS software and SWOG Statistical tools, respectively.^{51,52}

Protocol Version 4.0

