less than 1.2, the non-inferiority margin. The level of the confidence interval will be adjusted from 95% to account for type I error spending during interim efficacy analyses and will match the type I error used in the final analysis. If we achieve non-inferiority, then an additional test for superiority will be performed. The primary analysis will adjust for the stratification variables smoking status (current vs former) through the inclusion of a fixed effect and clinic with a random effect, respectively. A key secondary hypothesis is that the treatment effect will differ for current and former smokers. A test of interaction will be used to assess the heterogeneity of treatment effects (HTE) based upon smoking status (current vs former). Secondary analyses will be performed both adjusting for and investigating the HTE for key baseline characteristics including but not limited to 3 pre-specified comparisons: a history of asthma (yes vs no), gender (male vs female) and BMI (obese vs not obese).

Analysis of secondary outcomes by treatment group will employ negative binomial, logistic, linear and Cox proportional hazards models for event rates, binary outcomes, continuous outcomes, and time to event outcomes, respectively. Mixed effects models will be used to model outcomes with repeated measurements over time. Both unadjusted and adjusting models including the stratification variables (clinic and smoking status) as well as clinically important risk factors (e.g. history of asthma, gender, BMI, medication use) will be explored. Summary statistics, model estimates with confidence intervals and p-values will be used to present the findings. A large number of analyses, including HTEs, are planned and caution is necessary in interpreting the results especially since it is generally not possible to pre-specify all potential analyses. The number of secondary analyses explored will be clearly specified and the expected number of false positives will be calculated and included in the presentation of our results. Several methods of adjusting p-values for multiple comparisons exist; however, no clear consensus as to the most appropriate method is available. As recommended by Wang and Lagados, reporting will focus on point estimates and confidence intervals as well as p-values and reports will be considered hypothesis generating.⁴⁴

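### The final level of 0.04695 is the alpha left to spend, not a nominal test level, and section 3.2 also applies it to a non-inferiority test that has no interim look: a minor, conservative error

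*Protocol*

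**What the plan says.** Protocol section 3.5 (Interim Analysis) plans one formal look: "A single, formal, interim efficacy analysis will be performed once 50% of the information has been collected", that is, when "684 of the expected 1368 event of hospitalization or death have been observed". Stopping is allowed only if one treatment is shown superior; the trial, in its words, "it will not stop if the non-inferiority criteria are met". The levels are given as follows: "Based upon an O'Brien-Flemming type boundary", "the type I error rate would be 0.00305 for the interim analysis and 0.04695 at the final analysis", and the purpose is "to maintain a global 0.05 error rate over the course of the trial for the superiority comparison".

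Section 3.2 (Analysis Plan) decides non-inferiority by whether the upper confidence limit of the hazard ratio (azithromycin/roflumilast) lies below 1.2. It then says: "The level of the confidence interval will be adjusted from 95% to account for type I error spending during interim efficacy analyses", and that this level is to equal the type I error applied at the final analysis. A superiority test follows if non-inferiority is shown.

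Section 3.1 (Sample Size) states "92% power with a 1-sided type I error of 0.025 to establish non-inferiority", with margin 1.2 and a true hazard ratio of 1.

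**The concern.** Two things do not fit.

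First, 0.00305 and 0.04695 add to exactly 0.05. Alpha spent per stage adds up in this way. Nominal levels for successive tests do not, because a trial that crosses at the interim would often cross at the end as well. Section 3.2 nevertheless uses the final figure as a confidence level, so an analyst following the text would build a 95.305% interval.

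Second, the spending in section 3.5 protects the superiority comparison. Non-inferiority is tested once, at the end, yet its interval inherits the adjustment, and the resulting level differs from the one-sided 0.025 used for power in section 3.1.

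At stake is the threshold for the primary claim. The text supports a 95% interval (section 3.1) or a 95.305% interval (sections 3.2 and 3.5), and a correctly computed superiority level would give 95.10%. In an open-label trial this should be settled before outcome data are examined.

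**Working it through.** **Inputs.** From section 3.5: information fraction t = 684/1368 = 0.5, one interim plus a final analysis, O'Brien-Fleming-type boundary, overall two-sided 0.05. From section 3.1: margin 1.2, true HR 1, one-sided 0.025, 30% with an event at one year, 5% loss per year, 30 months of accrual plus 6 of follow-up, N = 3,200. Allocation is 1:1 (section 1.2).

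**1. Reproduce the plan's figures.** Lan-DeMets O'Brien-Fleming-type spending with 0.025 per side:

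- per side: 2 × [1 − Φ(2.2414/√0.5)] = 0.001525
- two-sided: 0.00305, critical value 2.963
- remainder: 0.05 − 0.00305 = 0.04695

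Both printed numbers come out exactly. The classical O'Brien-Fleming pair (0.0052 and 0.0480) does not match, so the spending-function version is the one in use. Exponential event times with hazard −ln(0.7) and uniform accrual give 1,367 to 1,369 events, against 1,368 stated.

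**2. Nominal final level.** Z₁ and Z₂ are bivariate normal with correlation √0.5 = 0.707. The final critical value c must satisfy

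P(|Z₁| ≥ 2.963) + P(|Z₁| < 2.963, |Z₂| ≥ c) = 0.05.

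The solution is c = 1.9686, a nominal two-sided level of 0.0490 (95.10% interval).

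**3. Error if 0.04695 is used as the level.** Then c = 1.9868 and the overall error is 0.0480. The new error at the final look is 0.0480 − 0.00305 = 0.0449. The other 0.0020 of the 0.04695 overlaps with trials that already crossed at the interim.

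**4. Does non-inferiority need an adjustment?** At true HR = 1.2, the interim statistic in favour of azithromycin has mean −ln(1.2) × √684/2 = −2.384. The chance of an early azithromycin-superiority stop is 1 − Φ(2.963 + 2.384), about 4.5 × 10⁻⁸. With the planned superiority stopping and a plain 95% final interval, the one-sided non-inferiority error is 0.02497. With the 95.305% interval it is 0.0234.

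**5. Effect on the non-inferiority decision at 1,368 events.**

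- Power = Φ(√1368 × ln(1.2)/2 − z) = Φ(3.372 − z)
- Largest passing observed HR = exp(ln 1.2 − 2z/√1368)

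| Interval | z | Power | Largest passing HR |
|---|---|---|---|
| 95% | 1.960 | 92.1% | 1.0793 |
| 95.10% | 1.969 | 92.0% | 1.0788 |
| 95.305% | 1.987 | 91.7% | 1.0778 |

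The 95% row reproduces the 92% in section 3.1. The log-scale half-width grows from 0.1060 to 0.1074, about 1.4%. Holding 92.1% power with the 95.305% interval would take about 1,390 events, 22 more than planned.

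**The case against.** Section 3.5 does not call its figures critical p-values. Read as alpha spent per stage, the pair is correct and sums to 0.05. The 95.305% interval is never printed; it comes from joining two sections, and exact boundaries are often left to a statistical analysis plan, which is not at hand here. A sponsor may also use one interval for both tests, at the level that superiority needs, and section 3.2 does so openly and gives its reason. An interval stricter than necessary is still valid. Both power figures round to the stated 92%.

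Most of this stands, and it limits the severity. It does not remove the point. Section 3.2 turns the final type I error into a confidence level, and 0.04695 is the only final figure the protocol offers, so the per-stage reading does not protect someone who follows the text. The non-inferiority level also differs from section 3.1, whatever the final superiority level turns out to be.

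A reader might go further and infer that type I error is inflated, that the non-inferiority interval is invalid, or that the trial is underpowered. The documents support none of these. An overall 0.0480 is below 0.05, 0.0234 is below 0.025, and the stated power survives rounding.

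**Conclusion.** Wrong as written, but minor and conservative. As a test level, 0.04695 leaves about 0.002 of the stated 0.05 unused (0.0480 attained); the nominal final superiority level is 0.0490. Carrying the superiority spending into the non-inferiority interval is valid but unnecessary, and it does not match section 3.1. The cost is about 0.4 percentage points of non-inferiority power and 0.0015 on the largest passing hazard ratio. Only an observed hazard ratio between 1.0778 and 1.0793 would change the conclusion, and then towards caution.

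This rests on the interim falling at exactly 50% information, 1,368 events at the final analysis, 1:1 allocation, the usual large-sample joint distribution of the log-rank or Cox statistics, and section 3.2 being applied literally with the 0.04695 of section 3.5.

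**What to change.** - **Section 3.5:** keep 0.00305 at the interim (critical value 2.963). State that 0.04695 is the alpha remaining, and give the nominal two-sided final level for superiority as 0.0490 (critical value 1.969). Add that it will be recomputed from the spending function at the actual information fraction.
- **Section 3.2:** judge non-inferiority on the two-sided 95% confidence interval (one-sided 0.025), as section 3.1 assumes, and confine the adjusted level to the superiority test.

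The cost is two sentences, with no change to the sample size, the data collected or the interim plan. The change should be made and dated before anyone sees outcome data by treatment group, because it slightly relaxes the non-inferiority threshold.

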4.1. Eligibility Criteria

The RELIANCE study is a randomized, multi-center pragmatic clinical trial, comparing the effectiveness of roflumilast vs. azithromycin in up to 3,200 patients with COPD at high risk of exacerbations. The study follow-up will be a minimum of 6 months and maximum of 36 months. Patients will receive a call at week 1, and will answer follow-up questionnaires at month 3 and 6, and thereafter, every 6 months until the patient achieves a primary outcome or the study ends. The eligibility criteria are intended to recruit a representative sample of “patients with severe COPD associated with chronic bronchitis and a history of exacerbations,” the FDA-approved indication for roflumilast in the U.S. and consistent with criteria established by the U.S. VA Pharmacy Benefits Management Services, and Medicare Part D benefits.^{58,59}

Eligibility criteria will be assessed based on standard clinical procedures with no requirements for specialized assessments, see section 1.4 for individual criteria. Exclusions are principally for safety, based on FDA or 2015 ACCP/CTS guideline or 2017 ERS/ATS guideline recommendations. During informed consent process, participants will be made aware that, should adverse effects occur, discontinuation or switching treatments are options to be discussed with the treating physician, and that they may drop out of the study without disrupting their receipt of routine healthcare. Clinical leads will be asked to exercise clinical judgment in the monitoring and reporting of adverse events to the IRB, FDA, and study through the RELIANCE Investigator. Neither the patient nor clinician will be masked to study treatment.

4.2. Data Sources

The primary sources of data for RELIANCE are regular interviews of enrolled patients, passive follow-up from EHRs and administrative databases, and ad hoc reporting from sites. Patient-reported outcomes will be collected online via the Participant Portal or, if the patient prefers, via telephone follow-up from the Call Center in English or Spanish, as preferred by the participant. Data on eligibility and occurrence of events will also be reported on the Investigator Portal. Deaths are often not well represented in EHRs, especially out-of-hospital deaths, so the NDI will be queried to determine vital status of all enrolled patients at the end of the trial. Data will also be collected on the subset of patients enrolled in Medicare from CMS administrative databases via collaboration with FDA Sentinel Program. When participants do not respond to regular attempts at contact and no death has been reported, a series of steps will be done to collect data on vital

Protocol Version 4.0

[figure not shown]

status including search and outreach by the Site Coordinator.

Data will be collected from various sources as outlined throughout the protocol (Participant Portal, Call Center Portal, Investigator Portal, EHR, and CMS administrative databases). The DCC will coordinate integration of these data throughout the study into the RELIANCE Database, which is housed at the DCC. The DCC will have real-time access to data keyed on the Investigator, Patient, and Call Center Portals. Follow-up data will be available to the DCC in real time and will be downloaded weekly. There will be intensive reviews of the Patient, Call Center, and Investigator Portal data on a weekly basis to review for missing data requiring follow-up from the patient, Call Center agent, or Investigator/Coordinator. The full database will be downloaded weekly to run reports on recruitment, retention, and missing data. These reports will be reviewed each week at the DCC and every other week during Executive Committee webinar meetings. Data queries will then be issued to sites and/or the Call Center for completion.

Please see Table 3, *Data Collection Schedule* for additional information on data collected from each source, and section 2.3. *Linkage with Medicare Data* for an overview of data transmission between CMS Administrative Databases and the RELIANCE databases.

Figure 3: RELIANCE Data Sources Overview

Protocol Version 4.0

4.3. Potential Risks

During this study, participants will continue to receive their usual care for COPD as per their treating physician. There are no additional evaluation procedures that patients will undergo to participate in the study. Patients will be asked to provide some information on their health history and current health status that is routinely collected in the process of medical care of patients with COPD. There are no significant physical risks from these procedures. As with all medical information, there is always the risk of psychological distress if PHI is not held confidential within the wishes of the participant. In order to minimize this risk, EHRs are held in HIPAA-2 compliant password-protected databases, and written information is stored in locked files or file-rooms when not attended by study personnel. Medical information is provided to treating sources consistent with HIPAA guidelines. If any medical illness requiring treatment is discovered during the collection of data for the course of this study protocol, individuals will be referred to their primary care providers for further evaluation and treatment.

Potential risks associated with this study are primarily those associated with the drugs under study, both of which are routinely used in clinical practice for this indication. As detailed in section 1.1, in completed trials of azithromycin for prevention of COPD exacerbations the most common reason for premature treatment discontinuation in the MACRO trial was hearing decrement, noted on audiograms performed by study personnel (azithromycin vs. placebo: 25 vs. 20% had hearing decrements, $p=0.01$).³⁷ Interestingly, hearing returned to baseline levels in a subsequent audiogram in roughly 1/3 of patients regardless of which group the patient was assigned to, azithromycin or placebo group, or if the study treatment was discontinued. Though no statistical test was reported and audiometry tests were not performed, self-reported hearing reduction in the BACE trial, was greater in the placebo group (4 vs 1% azithromycin).⁶⁹ No hearing-related adverse events were noted in the COLUMBUS trial, although audiometry tests were not part of the study protocol. Premature treatment discontinuation, noted in the MACRO trial due to adverse effects, was more common in the azithromycin group (33 vs. 28% placebo), however in the BACE trial it was more common in the placebo group (8 vs. 5% azithromycin).^{27,37,69} Macrolide resistance was also more common in the azithromycin group (81 vs. 41% placebo, $p < .0001$).⁶⁹ Other reasons for treatment discontinuation were less common and not significantly different between the azithromycin and placebo groups. These included: gastrointestinal, 1-2%; QTc prolongation (1 vs. 0.7% placebo), tinnitus, hearing decrements, allergic reaction, abnormal laboratory test, each $<1\%$.⁶⁹ In the BACE trial, there was no significant differences for positive sputum cultures with newly acquired pathogens, nor for

Protocol Version 4.0

macrolide-resistant bacteria during follow-up.³⁷

Macrolides (including azithromycin) are known to cause ventricular arrhythmias that could be fatal, but the incidence for long-term azithromycin use to prevent COPD exacerbations is unknown. On the basis of results published in an observational study using claims data, the FDA re-iterated the importance of carefully reviewing patient-level risk factors (history of prolonged QT interval, comorbid condition, or arrhythmogenic potential of other co-therapies) when using azithromycin.^{60,61} The incidence of arrhythmias with macrolides in the absence of additional risk factors is estimated to be very low, perhaps <1 in 100,000 individuals.

In a Cochrane review of placebo-controlled efficacy trials of roflumilast, premature treatment discontinuation due to adverse effects was more common with roflumilast than with placebo (15 vs. 9%, $p<0.05$; 9,511 patients).²⁸ The most common adverse effects that were also more common in the roflumilast group included diarrhea (10 vs. 3%, $p<0.05$), nausea (5 vs. 1%, $p<0.05$); weight loss (8 vs. 2%, $p<0.05$), psychiatric disorders (7 vs. 4%, $p<0.05$; includes anxiety, depression); and sleep disturbances/insomnia (3 vs. 1%, $p<0.05$). Mortality was low in the trials of roflumilast, with no significant difference between groups (roflumilast vs. placebo: 2 vs. 2%). A similar increase in adverse effect-associated treatment discontinuation was noted in comparative trials of up to 12 months in the REACT, RESPOND² and M2-124 and M2-12533 studies (12 vs. 8% placebo). The most common adverse effects that were also more common in the roflumilast group included diarrhea (17 vs. 6% placebo), weight loss (9 vs. 3% placebo). The OPTIMIZE study found that premature treatment discontinuation can be reduced by initiating treatment with a 4-week course of 250 mcg/day of roflumilast before dose-escalation to 500 mcg/day.

